5.3.2 Intended Study Enrollment

Definitions:

- **Study Donor:** an individual who has signed the informed consent form and is enrolled in the study.
- **Evaluable Study Donor:** an individual who is enrolled in the study, meets the inclusion criteria, and completes two Day 42 test periods.

This clinical trial requires enrolling a total of 93 evaluable study donors. However, due to the study design which incorporates a 2x2 crossover and the in vivo RBC recovery and survival substudy, the study will purposely enroll up to 100 study donors to account for study withdrawal, loss to follow-up and/or study donors who meet study criteria for the first donation of the crossover, but fail to meet study criteria for the second donation.

The study sites will make efforts to balance gender during screening.

Once enrolled, if a study donor's status should change from evaluable to non-evaluable per protocol definitions (see section 5.3.5), or if the study donor should discontinue follow-up (e.g., either voluntarily withdraw from the trial or become

Study Protocol

Clinical Investigation to Evaluate the New Health Sciences Hemanext® Oxygen Reduction System for Leukoreduced Red Blood Cells with CP2D Anticoagulant and AS-3 Additive - Pivotal Trial

Protocol #: CLIN-0001

Date: 28 Nov 2017

Page 15 of 65

lost to follow-up), then that study donor may be replaced in order to maintain intended study enrollment goals. Such replacement would increase the total number of enrolled study donors, but maintain the final number of evaluable study donors.

In instances where up to 100 study donors have been enrolled and all have undergone their first donation, consecutive donors will return for their second donation until a complete set of 93 matched data pairs have been obtained for both in vitro and, when applicable, in vivo parameters. As a result, it is possible that a study donor who donates an evaluable unit of whole blood will not be asked to return to provide a second unit of whole blood in instances where a complete data set has already been ascertained within the relative study arm.

Site A is not participating in enrolling donors for the in vivo cohort of the study. Site A will target enrollment of 40 evaluable donors for in vitro testing only. Site H will target enrollment 46 evaluable donors for in vitro testing of which 14 will also be enrolled for the cohort of in vivo testing. Site B target enrollment 14 evaluable donors for both in vivo and in vitro testing.

Table 3: Target Enrollment by site

Site	In vitro	In vivo
Site A: American Red Cross, Norfolk	40	0
Site B: Blood Center of Wisconsin	14	14
Site H: Hoxworth Blood Center	46	14
Total	100	28

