5.2 Study Primary Endpoints and Acceptance Criteria

The primary endpoints that will be evaluated in this clinical trial are RBC mass recovery, hemolysis and 24-hour in vivo red cell recovery. The endpoint-associated study acceptance criteria are listed below:

- A one-sided 95% lower confidence limit for the true proportion of packed RBC units with hemolysis at day 42 of < 1% is > 95%.
- The mean 24-hour, post-transfusion, in vivo red cell recovery of at least 75% with a standard deviation of $\leq 9\%$, and the lower limit of a one-sided 95% confidence interval for the population proportion of successes is $\geq 70\%$.
- Red Blood cell recovery $\geq 85\%$; with 95% confidence that at least 95% of units are $\geq 85\%$.

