5.3 Donor/Data Criteria**5.3.1 Sample Size**

The sample sizes described within the protocol were selected to demonstrate meeting study primary endpoints that conform to the FDA's 95-95 rule (95% confidence and 95% reliability). For successful endpoint outcomes, the study requires meeting the acceptance criteria in 92 of 93 test units per test condition. Therefore, 93 evaluable study donors will complete the study. In the event of two (2) donors/units with unmet acceptance criterion occurring out of ninety-three (93) evaluable procedures (i.e., within one or more study arm(s) for one or more acceptance criteria/primary endpoints), the study will be discontinued.

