5.3.5 Evaluable and Non-Evaluable Whole Blood Collections

Collected whole blood's evaliability status per protocol definition (see section 5.3.5.1) will determine whether these data are included within the data set that will be analyzed towards study endpoints. Blood donations deemed unevaluable per protocol definition will necessitate whole blood sample replacement obtained from alternate evaluable study donors such that intended population targets are maintained.

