- **Protocol Deviation:** Any procedural protocol deviation that the PI and/or sponsor determine(s) has the potential to impact (both positively and negatively) any acceptance criteria, study endpoint and/or analytical study-critical outcomes will result in a determination of non-evaluability. Procedural protocol deviations must be documented within the eCRFs and all deviations that compromise data validity (i.e., one that impacts evaluability) must be reported to the sponsor within 24 hours (see section 9.3). Examples of protocol deviation that have the potential to impact study outcomes include but are not limited to the following: (1) storage deviation (e.g., electrical outage and unknown storage conditions, unit left out of refrigeration for >30 minutes, sample frozen vs. refrigerated, etc.), (2) incorrect mixing/agitation (e.g., unit dropped from height, unit inappropriately mixed prior to sampling, excess sample drawn into syringe and quickly re-injected back into unit, etc.), (3) other deviation (e.g., incorrect

Study Protocol

Clinical Investigation to Evaluate the New Health Sciences Hemanext® Oxygen Reduction System for Leukoreduced Red Blood Cells with CP2D Anticoagulant and AS-3 Additive - Pivotal Trial

Protocol #: CLIN-0001

Date: 28 Nov 2017

Page 19 of 65

centrifuge speed/duration, other)). Deviations must further be communicated to the respective IRB per local regulations.

- **Sickle Cell Trait:** Any whole blood unit in the study from a sickle cell trait (SCT) positive study donor will be excluded.
- **Grossly Lipemic Specimens:** Any whole blood unit grossly evaluated (per visual inspection) as lipemic will be non-evaluable relative to only the RBC hemolysis endpoint at Day 42. Any units in question will be reviewed by the PI or designee and if considered non-evaluable, the unit will be removed from the study, and the study donor may be replaced.
- **Positive Bacterial Culture:** This evaluability determination pertains only to study donors who participate in the in vivo portion of the study. Should the outcome of the pre-infusion bacterial culture (see section 6.2.16.11) indicate that the stored LRRBCs are '+' for bacteria, then the unit will be discarded. As a result, the study donor and his/her unit of blood will be non-evaluable and the study donor may be replaced.

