Clinical Investigation to Evaluate the New Health Sciences Hemanext® Oxygen Reduction System for Leukoreduced Red Blood Cells with CP2D Anticoagulant and AS-3 Additive - Pivotal Trial

[figure not shown]
Protocol #: CLIN-0001

Date: 28 Nov 2017

Page 64 of 65

Note: If flatbed agitator shelf is less 36 x 76 x 2.5 cm, please place one Hemanext RBC Processing System as shown in Figure 3 below.

Figure 3

- 14) Make sure the agitator shelf is fully closed. If applicable, make sure the incubator doors are closed. Note: limit the amount of times the agitator doors are opened and remain open during processing.
- 15) Leave Hemanext RBC Processing System on the agitator shelf for 3 hours +/- 15 minutes for O₂/CO₂ reduction.
- 16) After 3 hours, remove the Hemanext RBC Processing System from the agitator shelf. Note: confirm that the O₂ indicator in the ORB is pink.

- 17) Hang ORB at head height of no greater than 72 inches.
- 18) Open clip on the ORB blood line and the HSB blood line. Transfer the LR RBC O₂/CO₂ reduced into the HSB.
- 19) Once all volume has been transferred to the HSB, close the clip on the HSB blood line and heat seal the tubing immediately after the white over sleeve section. (Caution: Do not close clip on white over sleeve section. Do not heat seal tubing in the white over sleeve section)
- 20) Remove the ORB and dispose accordingly.
- 21) Segment bloodline as needed.
- 22) Place HSB into cold storage of 1 to 6° C for up to 42 days after collection.
- 23) When pulling from cold storage, confirm that the O₂ indicator in the HSB is pink.

STORAGE AND HANDLING

- Do not use if:

Study Protocol

Clinical Investigation to Evaluate the New Health Sciences Hemanext® Oxygen Reduction System for Leukoreduced Red Blood Cells with CP2D Anticoagulant and AS-3 Additive - Pivotal Trial

Protocol #: CLIN-0001

Date: 28 Nov 2017

Page 65 of 65

- Tamper evident package has been opened
- Signs of deterioration are visible
- The fluid path closures are loose or not intact
- The package is damaged
- The ORB, which contains RBC, is dropped on a hard surface (e.g. floor, lab bench, etc.)
- Store at room temperature
 - Avoid exposure to excessive heat
 - Protect from freezing

SYMBOL LEGEND	
	Symbol for Manufacturer
 YYYY-MM	Symbol for Date of Manufacture
LOT XMMNN	Lot Number
	Symbol for Sterile Fluid Path
	Symbol for Single Use Only
	Symbol for Refer to Instructions for Use

CONTACT INFORMATION

New Health Sciences, Inc.
[name]

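### No rule counts a test unit lost to the device before Day 42 as a failure, so total losses drop out of the 92-of-93 acceptance count

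*Combined protocol and SAP*

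**What the plan says.** **Criteria.** Section 5.2 asks for hemolysis that "A one-sided 95% lower confidence limit for the true proportion of packed RBC units with hemolysis at day 42 of < 1% is > 95"%. It also asks for RBC recovery of at least 85%, "with 95% confidence that at least 95% of units are" at or above that value.

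**Decision rule.** Under section 5.3.1 the sample sizes are meant to "conform to the FDA's 95-95 rule (95% confidence and 95% reliability"), and "the study requires meeting the acceptance criteria in 92 of 93 test units per test condition". Two failures among the 93 evaluable procedures discontinue the study. Section 5.4 repeats the rule as 93 evaluable procedures with at most one failure.

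**Who is counted.** Section 5.3.2 defines an evaluable donor as "an individual who is enrolled in the study, meets the inclusion criteria, and completes two Day 42 test periods". Up to 100 donors are enrolled, and they return consecutively until there are 93 matched pairs. The surplus is explained by withdrawal, loss to follow-up and failure to qualify for the second donation. Device loss is not mentioned.

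**What is replaced.** Section 5.3.5 says "Blood donations deemed unevaluable per protocol definition will necessitate whole blood sample replacement". Section 5.3.5.1 lists the causes: transmissible-disease positivity, slow or incomplete collection, procedural deviations judged influential by the principal investigator or sponsor, sickle cell trait, gross lipemia (hemolysis only) and positive bacterial culture (in vivo cohort only). After a positive culture, "the study donor and his/her unit of blood will be non-evaluable and the study donor may be replaced". Partial data are reported descriptively.

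**RBC recovery.** The standard equation in section 6.2.14 (Figure 4) uses a post-Hemanext hematocrit or count, but labels the volume beside it as post-filtration.

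**The concern.** The sponsor wants to conclude that at least 95% of units made with this system meet the criteria. The definition of an evaluable donor makes the denominator depend on the unit surviving the device under test. A bag that leaks out, or a transfer that fails completely, leaves nothing to test on Day 42. The donor then does not meet the section 5.3.2 definition, and another donor completes the set of 93.

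Such a loss is arguably the clearest way for a processing and storage system to fail, yet no failure count includes it. This applies to the acceptance rule and equally to the two-failure discontinuation rule. RBC recovery is affected too. Its value is settled on Day 0-1, but the donor enters the count only after two Day 42 periods.

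Leaving such units out can only raise the estimated success proportion. The rule tolerates one failure, so one or two uncounted losses are enough to change the result.

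**Working it through.** **1. Inputs.** Reliability target 0.95, one-sided confidence 95%, 93 evaluable units, at most one failure (sections 5.2, 5.3.1, 5.4). The documents give no device-loss rate, so any rate used below is an assumption.

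**2. Reproduce the plan's figure.** If true reliability is exactly 0.95, the chance of passing is

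P(X ≥ 92 | n = 93) = 0.95^93 + 93 × 0.05 × 0.95^92 = 0.04998.

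This is just under 0.05. For 91 of 92 the value is 0.0521, so 93 is the smallest size that allows one failure. The exact one-sided 95% lower limit for x successes in n is the 5th percentile of Beta(x, n − x + 1). For 92/93 it is 0.950006. The plan's arithmetic is correct. The gap lies in what enters n.

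**3. Follow a totally lost test unit through the text.**
- Section 5.3.5.1 does not list leak, seal failure or transfer failure.
- Section 5.3.2 requires two completed Day 42 periods, which this donor cannot supply.
- Sections 5.3.1 and 5.4 count evaluable procedures only.
- Section 5.3.2 brings donors back until 93 pairs exist, so another donor fills the place.
- Section 5.3.5.1 keeps partial data for descriptive statistics.

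No step records a failure.

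**4. Count losses as failures.** Each lost unit is added to the denominator as a non-success.

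| Measured failures among 93 | Device losses | Plan reports | Losses counted | Lower limit | Exceeds 95%? |
|---|---|---|---|---|---|
| 0 | 0 | 93/93 | 93/93 | 96.83% | yes |
| 0 | 1 | 93/93 | 93/94 | 95.05% | yes |
| 0 | 2 | 93/93 | 93/95 | 93.52% | no |
| 1 | 0 | 92/93 | 92/93 | 95.0006% | yes |
| 1 | 1 | 92/93 | 92/94 | 93.45% | no |
| 1 | 2 | 92/93 | 92/95 | 92.04% | no |

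Two failures in total become acceptable only from n = 124, beyond the 100 donors planned.

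**5. Illustrate the likelihood.** With an assumed loss probability q per unit, the chance of at least two losses in 95 processed test units is 1 − (1 − q)^95 − 95q(1 − q)^94. This gives 0.246 at q = 1%, 0.569 at q = 2%, and zero at q = 0.

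**6. Partial losses.** A unit that loses some volume but is still tested on Day 42 stays in the count. Whether it registers as low recovery depends on the volume term in section 6.2.14. If that volume is measured after Hemanext processing, the lost cells lower the recovery. If it is the filtered whole-blood volume, as labelled, volume lost in the ORB does not enter the equation. Pairing a hematocrit taken after plasma removal and AS-3 addition with a whole-blood volume does not give the red cell mass of any one container, so the label may be a slip. The text does not settle it.

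**The case against.** **Exclusion of leaks is inferred.** Section 5.3.5.1 does not name leak or transfer failure, and the replacement sentence in section 5.3.2 refers to section 5.3.5 or to a donor who discontinues. This is correct: the plan never says in so many words that a leaked unit is dropped and replaced. But the Day 42 definition and the return of donors until 93 pairs exist have that effect, and silence leaves the choice until after the event. Section 5.4 announces a separate SAP, which is not among the documents. Evaluability is defined in the protocol, so the correction belongs there.

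**The hemolysis criterion concerns Day 42.** A destroyed unit has no Day 42 hemolysis value. This stands, and it is why the wider denominator should be a supporting analysis for hemolysis and not replace the primary one.

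**Losses would be visible.** All enrolled donors are reported (5.4, 10.1), product accountability is complete (6.1.1), IFU deviations in processing are recorded (6.2.16.9), and out-of-range recoveries reach the sponsor within 24 hours (6.2.13). This disclosure is real, but it does not touch the acceptance count.

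**Stronger readings that the documents do not support.** A reader might infer that device losses never count; partial losses tested on Day 42 do stay in. A reader might infer that a unit losing most of its cells in the ORB fails the 85% criterion by definition; that depends on the unsettled volume term. A reader might class contamination as device loss. The culture rule covers only in vivo units (target 28) and does not attribute a positive result to the device. Finally, the IFU asks staff to act as follows: "When pulling from cold storage, confirm that the O₂ indicator in the HSB is pink". No such data item appears in the Day 21 or Day 42 lists, but indicator colour is not an acceptance criterion and SO₂ is measured at both times, so recording it would change no count.

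**Conclusion.** The point holds for test units totally lost to the ORB or HSB before Day 42. Under the section 5.3.2 definition they leave the 92-of-93 rule, and nothing counts them as failures. The sample-size arithmetic is sound.

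With losses counted as failures, a single loss with no measured failure does not change the conclusion. One loss plus one measured failure, or two losses, would move the limit from at least 95.0006% to about 93.5%.

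This rests on two assumptions: that each lost unit is a failure, and that losses occur at all. For RBC recovery, a unit lost from the HSB after an adequate Day 0-1 measurement would count as a success, so the table is the unfavourable end for that endpoint. If no unit is lost, the results are identical. The protocol should be corrected because its own definition makes the acceptance count depend on the device not having failed.

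**What to change.** In sections 5.3.2 and 5.3.5.1:

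- **(a) RBC recovery.** State that a test unit transferred to the ORB and then lost through device leak, seal failure or transfer failure is counted in the RBC recovery rule. Base its recovery on the post-Hemanext volume that reached the HSB, and apply the exact limit to the enlarged denominator. Align the volume term in Figure 4 (section 6.2.14) with this. Say whether such a unit also counts toward the two-failure discontinuation rule in section 5.3.1.
- **(b) Hemolysis.** Keep the 93-unit analysis. Beside it, report a supporting exact one-sided 95% lower limit with all test units transferred to the ORB as denominator and device-caused losses as failures.
- **(c) Recording.** Add eCRF fields for device malfunction and cause of loss. Attribute the cause without knowledge of the endpoint result, for example by fixed categories completed at the time of the event. Report culture-positive test units separately, by number and cause.

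Replacement without counting stays for causes unrelated to the device.

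The cost is protocol wording, two eCRF fields and one extra analysis line. The downside for the sponsor is that the RBC recovery count and the supporting limit may be slightly less favourable.

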5.3.3 Inclusion/Exclusion Criteria

The study donor must conform to the criteria listed in Table at the time of study donor selection and must meet study eligibility in order to participate in the study. Any deferral criteria will be based on local procedures and SOPs. Note, further, that later evaluability determinations (see section 5.3.5) may impact study-eligible individuals' eligibility/evaluability and/or full participation within the study.

Study Protocol

Clinical Investigation to Evaluate the New Health Sciences Hemanext® Oxygen Reduction System for Leukoreduced Red Blood Cells with CP2D Anticoagulant and AS-3 Additive - Pivotal Trial

Protocol #: CLIN-0001

Date: 28 Nov 2017

Page 16 of 65

Table 4: Inclusion/Exclusion criteria

Inclusion Criteria	Criteria to qualify for Inclusion	Reference
Age	Study donor must be \geq 18 years of age.	Age of legal consent used for inclusion criteria.
Weight	Study donor must be \geq 110 pounds.	AABB Standards for Blood Banks and Transfusion Services 28 th Edition
Temperature	Study donor's body temperature must be \leq 37.5°C / 99.5°F (oral).	
Hemoglobin	Study donor's hemoglobin must be \geq 12.5 g/dL if female and \geq 13.0 g/dL if male.	FDA Standard 21CFR 640.3(b)(3). Study participants must meet EITHER hemoglobin or hematocrit criteria.
Hematocrit	Study donor's hematocrit must be \geq 38% if female and \geq 39% if male.	
Donor Eligibility	Study donor must meet all criteria per respective site's Research Blood Donation Record (BDR).	Site documentation
Prior Donation	
Study donor's most recent single RBC unit donation must have been \geq56 days prior to study donation.
 
Study donor's most recent double RBC unit donation must have been \geq 112 days prior to study donation.
 
Only donors who participate in the in vivo portion of the study:
 
An additional 2-4 weeks between donations will be required to ensure washout from prior in vivo survival procedures.
	AABB Standards for Blood Banks and Transfusion Services 28 th Edition
Informed Consent	Study donor must have consented to study participation by reviewing and having expressed understanding the site-respective IRB-approved informed consent form prior to undergoing any study related procedures.	ISO 14155:2011 21 CFR 50
Blood-borne Pathogens	Study donor's testing results from collected blood does not indicate a risk of transfusion-transmitted disease (TTD)*.	N/A
Adverse Events	Study donors must agree to report adverse events from the time of signing the informed consent to twenty-four hours following the end of their active study involvement.	N/A
Pregnancy	Female study donors must not be pregnant or expected to be pregnant. For donors participating in the in vitro portion, this is an interview question only.	N/A

Study Protocol

Clinical Investigation to Evaluate the New Health Sciences Hemanext® Oxygen Reduction System for Leukoreduced Red Blood Cells with CP2D Anticoagulant and AS-3 Additive - Pivotal Trial

Protocol #: CLIN-0001

Date: 28 Nov 2017

Page 17 of 65

	
Only female donors who participate in the in vivo portion of the study: Women of child-bearing age must not be pregnant, as determined by a negative pregnancy test prior to each re-infusion, or be breastfeeding. If acceptable by local procedures, post-menopausal or surgically sterile women may be exempt from the pregnancy testing requirement.
	
--	--	--

**Study donors' TTD test results may not be available until several days following enrollment and donation of a whole blood unit. See section 5.3.5 for additional details.*

For the purpose of this trial, not meeting any of the inclusion criteria constitutes exclusion from the trial (i.e., meeting exclusion criteria).

5.3.4 Donor Withdrawal Criteria

Any study donor that enrolled in the study can withdraw from the study, effectively withdrawing consent, at any time, for any reason, without prejudice or consequence. Study donors are to be informed that they are free to leave the study at any time for any reason without prejudice or consequence in the informed consent document. A study donor may withdraw from the study at any time following blood donation and thus withdraw permission to evaluate their blood product.

If a study donor withdraws from the study, whether prior to completion of the whole blood donation or after completion of the whole blood donation, the data collected up through the time of withdrawal (including testing results) will be included within the study database. Withdrawn study donors will be replaced in all instances where incomplete data required to calculate acceptance criteria result from their withdrawal. If a study donor withdraws at a point when both the whole blood collection and all study analyses are complete, then their withdrawal does not impact the data's entry into the database, their data will be analyzed within the full data set and the study donor will not be replaced.

